9.1.4.2 Safety and tolerability assessments

Safety will be monitored by the assessments described below as well as the collection of AEs at every visit. For details on AE collection and reporting, refer to Section 7. Significant

findings that were present prior to the signing of informed consent must be included in the relevant medical history/current medical conditions in the clinical trial record. Significant new findings that begin or worsen after informed consent must be recorded in the clinical trial record.

9.1.4.3 Physical examination

Physical examinations will include an examination of general appearance, skin, neck (including thyroid), eyes, ears, nose, throat, lungs, heart, abdomen, back, lymph nodes, extremities, and a basic nervous system evaluation. Information about the physical examination will be present in the source documentation. For the assessment schedule refer to Table 9-1.

Significant findings that were present prior to the signing of informed consent must be included in the clinical trial record. Significant new findings that begin or worsen after informed consent must be recorded in the clinical trial record. Findings related to tumor do not need to be reported.

9.1.4.4 Vital signs

Vital signs include body temperature, blood pressure and pulse measurements. Blood pressure (systolic and diastolic) and pulse should be measured.

For the assessment schedule refer to Table 9-1.

9.1.4.5 Height and weight

Height in centimeters (cm) and body weight (to the nearest 0.1 kilogram [kg] in indoor clothing, but without shoes) will be measured. Height will be measured at screening only. For the assessment schedule for weight refer to Table 9-1.

9.1.4.6 Performance status

ECOG performance status will be assessed as per the assessment schedule (refer to Table 9-1).

Assessment of ECOG performance status (Table 9-2) will be performed within the time windows described above of the scheduled assessment, even if study medication is being held. More frequent examinations may be performed at the investigator's discretion, if medically indicated.

Table 9-2 ECOG Performance status scale

Score	Performance Status
1	Restricted in physically strenuous activity but ambulatory and able to carry out work of a light or sedentary nature, e.g. light housework, office work
2	Ambulatory and capable of all self-care but unable to carry out any work activities. Up and about more than 50% of waking hours
3	Capable of only limited self-care, confined to bed or chair more than 50% of waking hours
4	Completely disabled. Cannot carry on any self-care. Totally confined to bed or chair
5	Dead

9.1.4.7 Laboratory evaluations

Local site laboratories will be used for the analysis of scheduled hematology, biochemistry, urine, and other blood specimens collected as part of safety monitoring. All unscheduled blood testing will be performed locally, with exceptions for emergency conditions. The time windows granted for laboratory evaluations are identical to the corresponding visit time windows for each visit (refer to Section 9.1).

Laboratory abnormalities that are considered clinically significant, induce clinical signs or symptoms, require concomitant therapy or require changes in study treatment constitute an adverse event (AE) and must be reported as an AE in the clinical trial record.

Laboratory values obtained at the screening visit will be used to assess eligibility to meet

inclusion criteria. In addition, eligible patients must have baseline laboratory assessments performed on Cycle 1 Day 1 or within 24 hours prior to dosing.

Table 9-3 Local Clinical laboratory parameters collection plan

Test Category	Data Results	Test Name
Hematology		Hgb, platelets, white blood cells (WBC), red blood cells (RBC), differential (basophils, eosinophils, lymphocytes, monocytes, neutrophils (% or absolute))
Chemistry		Albumin, ALT, AST, calcium, creatinine, total bilirubin, blood urea nitrogen (BUN) or urea, potassium, sodium, glucose.
Creatinine clearance		Creatinine clearance will be calculated using the serum creatinine value.
Pregnancy test		At screening visit, serum pregnancy test will be performed. Following the screening assessment, urine pregnancy tests should be performed. Pregnancy test must be performed according to the date windows listed under schedule of assessments. If local requirements dictate otherwise, local regulations should be followed

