7.4 Adverse Event Reporting

For guidance on reporting adverse events, refer to the [Adverse Event SOP](#). Please modify the below template language as needed.

Adverse events will be graded according to CTCAE v5. Both Serious and Non-Serious Adverse Events will be clearly noted in source documentation and listed on study specific Case Report Forms (CRFs). The Protocol Director (PD) or designee will assess each Adverse Event (AE) to determine whether it is unexpected according to the Informed Consent, Protocol Document, or Investigator's Brochure, and related to the investigation. All Serious Adverse Events (SAEs) will be tracked until resolution, or until 30 after the last dose of the

study treatment.

SAEs CTCAE Grade 3 and above, and all subsequent follow-up reports will be reported to the Stanford Cancer Institute Data and Safety Monitoring Committee (DSMC) using the study specific CRF regardless of the event's relatedness to the investigation. It is the Investigator and study team's responsibility to report events meeting the IRB definition of 'Unanticipated Problem' to the IRB using eProtocol within 10 working days, or within 5 working days for deaths or life-threatening experiences.

No specific safety precautions or adverse event reporting guidance is required to the manufacturer. Follow standard precautions and reporting as below. Additional information is available in the Package Insert: https://www.accessdata.fda.gov/drugsatfda_docs/label/2017/208716s000lbl.pdf

For other participating sub-sites, non-serious grade 1 and 2 adverse events will be reported to the participating sites in regular conference calls. All adverse and serious adverse events should be recorded into the RedCap eCRF. All Serious Adverse Events (Grade 3 or above as graded by CTCAE v 5) will additionally be reported to the overall PI of the study at Stanford in writing within 24 hours of learning the event and to [contact]. The participating sub-site will also report to Eli Lilly as described at the end of this section. Stanford will promptly report SAEs to CCTO for forwarding as necessary to the Stanford IRB and DSMC; the participating sub-site will notify their IRB per their SOP. Any death associated with the use of investigational agents or devices will prompt suspension of further patient enrollment into the trial from all sites until the cause of death is investigated by the principal investigator from the respective site and the overall PI of the study at Stanford.

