Regulatory and reporting requirements

It is the responsibility of the investigator to document all adverse events which occur during the investigation. An adverse event is any untoward medical occurrence in a patient or clinical investigation subject, temporally associated with the use of the medicinal product, whether or not considered related to the medicinal product. *An AE can therefore be any unfavorable and unintended sign (including an abnormal laboratory finding), symptom, or disease (new or exacerbated) temporally associated with the use of a medicinal product.* Anticipated day-to-day fluctuations of the disease under study that do not represent a clinically significant exacerbation or worsening need not be considered an adverse event.

In addition, any SAEs which occur as a result of protocol specific diagnostic procedures or interventions must also be reported.

(a) *Definition of Serious Adverse Events*

A serious adverse experience is any event which is fatal, life threatening, disabling or incapacitating or results in hospitalization, prolongs a hospital stay or is associated with congenital abnormality. In addition, any experience which the investigator regards as serious or which would suggest any significant hazard, contraindication, side effect or precaution that may be associated with the use of the drug should be reported as a serious adverse event. Examples of such events are invasive or malignant cancers, intensive treatment in an emergency room or at home for allergic bronchospasm, blood dyscrasias or convulsions that do not result in hospitalization, or development of drug dependency or drug abuse.

Abnormal laboratory findings (e.g., clinical chemistry, hematology) or other abnormal assessments (e.g., x-rays, scans, vital signs, etc.) that are judged by the investigator as **clinically significant** will be recorded as AEs or SAEs if they meet the definition of an AE or SAE.

Life threatening definition:

An adverse event is life threatening if the patient was at immediate risk of death from the event as it occurred (i.e. it does not include a reaction that if it had occurred in a more serious form might have caused death). For example, drug-induced hepatitis that resolved without evidence of hepatic failure would not be considered life threatening even though drug-induced hepatitis could be fatal.

Disability/incapacitating definition:

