12.5.2 Analysis Plan

Overall survival (OS) is defined as the time from start of treatment to death due to any cause. If a subject is not known to have died, then OS will be censored at the latest date the subject was known to be alive. The OS distribution will be estimated using the Kaplan-Meier method, and the Kaplan-Meier curves, medians and 95% confidence intervals of the medians will be presented.

Progression-free survival is defined as the time from start of treatment to date of progression or death due to any cause. If a subject is not known to have progressed or died, then PFS will be censored at the latest date the subject was known to be alive or disease-free. The PFS distribution will be estimated using the Kaplan-Meier method, and the Kaplan-Meier curves, medians and 95% confidence intervals of the medians will be presented.

In addition, we will estimate response duration using Kaplan-Meier methods.

For all safety analyses, the safety set will be used. Toxicities will be dichotomized as none versus any adverse event, or none and mild versus moderate to severe adverse event.

Summary tables for adverse events (AEs) will include only AEs that started or worsened during the on-treatment period, the treatment-emergent AEs, unless otherwise specified.

All safety data collected in the study will be listed regardless of the study period with data collected during the pre-treatment and post-treatment period flagged. The incidence of treatment-emergent adverse events (new or worsening from baseline) will be summarized by system organ class and or preferred term, severity (based on CTCAE grades), type of adverse event, relation to study treatment by the Principal Investigator and/or research team.

Deaths reportable as SAEs and non-fatal serious adverse events will be listed by patient and tabulated by type of adverse event.

Specific safety event categories (SEC) will be considered. Such categories consist of one or more well-defined safety events which are similar in nature and for which there is a specific clinical interest in connection with the study treatment(s).

For each specified category, number and percentage of patients with at least one event per category will be summarized.

Handling of missing values/censoring/discontinuations

All attempts will be made to ensure that the database contains complete information. No imputation will be applied for missing data.

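### Laboratory harms are tabulated only through recorded adverse events, so any-grade rates of silent low-grade cytopenias and ALT/AST rises may be understated

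*Combined protocol and SAP*

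**What the plan says.** Safety is a secondary objective (Sections 1.2 and 10.2). The planned summary is in Section 12.5.2: "The incidence of treatment-emergent adverse events (new or worsening from baseline) will be summarized by system organ class and or preferred term", broken down further by CTCAE severity and relation to treatment. The same section adds: "Toxicities will be dichotomized as none versus any adverse event, or none and mild versus moderate to severe adverse event". For everything else it says: "All safety data collected in the study will be listed regardless of the study period". Nothing in Section 12 plans CTCAE grading of laboratory values, a worst-grade table or a shift table. Section 12.5.2 also mentions specific safety event categories but neither names them nor ties any to laboratory values.

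Whether a laboratory change reaches the adverse event tables depends on these rules:

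- Section 9.1.4.7 sets four triggers for mandatory reporting: "Laboratory abnormalities that are considered clinically significant, induce clinical signs or symptoms, require concomitant therapy or require changes in study treatment constitute an adverse event".
- Section 7.4 provides for recording of "Abnormal laboratory findings (e.g., clinical chemistry, hematology) or other abnormal assessments" where the investigator judges them clinically significant.
- The general definition in Section 7.4 is wider: "An AE can therefore be any unfavorable and unintended sign (including an abnormal laboratory finding), symptom, or disease (new or exacerbated".
- Section 7.4 also states "All adverse and serious adverse events should be recorded into the RedCap eCRF" and that "non-serious grade 1 and 2 adverse events will be reported to the participating sites in regular conference calls".

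**The concern.** The laboratory toxicities in question are the drug's own. Section 7.3.5 treats causality as established for neutropenia, leukopenia, anemia and thrombocytopenia, and Section 7.3.4 treats ALT/AST elevation as an adverse drug reaction. Counts and chemistry are measured on a fixed schedule at every site (Table 9-1, including day 14 of cycles 1 and 2), so the incidence of each grade could be read from objective data. The plan instead reports it through a filter of investigator judgement with no grade threshold, at more than one site.

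An unrecorded low-grade event can only lower the tabulated rate. The none-versus-any summary is the most exposed, since a single mild event changes a patient's category. At stake is the accuracy of low-grade laboratory toxicity rates and their comparability between investigators. The primary endpoint, the futility rule and the criterion for a larger study (Section 12.7) all use response and are not touched.

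**Working it through.** The plan states no laboratory toxicity rate, so there is no figure to reproduce. The check is textual first, then arithmetic on the denominators.

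**Step 1. Which changes must be recorded.** Setting the dose rules against the four triggers in Section 9.1.4.7:

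| Laboratory change | Dose action | Recording forced by a treatment change? |
|---|---|---|
| Grade 1 or tolerable Grade 2 cytopenia | None (Section 6, Table 7-5) | No |
| Grade 1, or transient Grade 2, ALT/AST without the bilirubin criterion | None (Table 7-3) | No |
| Intolerable Grade 2 | Interrupt (Section 6) | Yes |
| Persistent or recurrent Grade 2 ALT/AST, or Grade 2 or higher with the bilirubin criterion | Suspend or discontinue (Table 7-3) | Yes |
| Grade 3 or 4 | Suspend or discontinue (Section 6, Tables 7-3 and 7-5) | Yes |

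For the first two rows, a change that is also asymptomatic and untreated leaves only the clinical-significance trigger, which is a judgement. The concern is confined to those two rows.

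**Step 2. Effect on the per-toxicity any-grade rate.** Section 12.6.2 gives N = 17, or 9 if the trial stops after stage 1. If k patients have their only event of a given toxicity unrecorded, the rate falls by k/N:

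- k = 1: 1/17 = 5.9 points; 1/9 = 11.1 points
- k = 2: 2/17 = 11.8 points; 2/9 = 22.2 points
- a patient with another recorded event of the same toxicity: 0

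**Step 3. Effect on the two splits.** Taking mild as Grade 1, an unrecorded Grade 1 event does not move the none-and-mild versus moderate-to-severe split. An unrecorded Grade 2 event moves it by 1/17 or 1/9, and only if the patient has no other recorded event of that toxicity at Grade 2 or above. If none-versus-any is pooled over all adverse events, little changes, because Section 7.3.1 expects diarrhea in most patients.

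**Step 4. Illustration (assumed counts).** Suppose 6 of 17 patients have a low-grade cytopenia and 2 are unrecorded. With exact (Clopper-Pearson) 95% intervals:

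- true: 6/17 = 35.3% (14.2 to 61.7)
- tabulated: 4/17 = 23.5% (6.8 to 49.9)

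**Step 5. Range under assumed capture.** Let L be the share of affected patients with only silent low-grade changes and q the chance that such a change is recorded. Then reported rate = true rate × [(1 − L) + L × q]. The documents give none of these inputs. Over true rates of 40% to 80%, L of 0.5 to 0.75 and q of 0.25 to 0.75, the extremes are:

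- smallest shortfall: 40% × (0.5 + 0.5 × 0.75) = 35%, a loss of 5 points
- largest shortfall: 80% × (0.25 + 0.75 × 0.25) = 35%, a loss of 45 points

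With q = 1 the loss is zero. The width of this range reflects the assumptions; it is not evidence of a loss of any particular size.

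**The case against.** The strongest reply is that the recording gap is inferred. Section 9.1.4.7 lists conditions that are sufficient for reporting and never says they are the only ones. The definition in Section 7.4 expressly admits an abnormal laboratory finding, all adverse events are to be recorded, and sharing of Grade 1 and 2 events is expected. A careful investigator could record every low-grade change. This stands as far as it goes: recording is permitted. But the definition is permissive, the same section then brings in clinical significance, and an instruction to record all adverse events does not settle which laboratory changes count as one.

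Second, the plan promises an analysis of adverse events and delivers it; no section promises a laboratory rate. That is true, so this is an improvement to the analysis and not a broken commitment.

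Third, a listing covering 9 or 17 patients can be counted by hand, and the safety event categories could be defined on laboratory grades. Both are possible, but a listing helps only if the values are entered and still yields no planned rate, and the plan does not define the categories.

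Fourth, no decision changes. The management tables act on the laboratory values whether or not an adverse event is recorded, and the go-forward criterion is response. This stands and limits the severity.

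**Conclusion.** The concern holds as a minor point. As written, the only planned rates for cytopenias and ALT/AST rises come from recorded adverse events, and no section clearly requires recording of an asymptomatic, untreated low-grade change. Any resulting error in the any-grade rates is downward. Its size is unknown: 5.9 points per affected patient at N = 17, or 11.1 at N = 9, for a per-toxicity rate and only where the patient has no other recorded event of that toxicity. Intolerable Grade 2 events, persistent or recurrent Grade 2 ALT/AST rises and Grade 3 or 4 events are outside the concern.

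The conclusion assumes that some investigators will not record every low-grade change, which the documents allow but do not establish. The wide overlap of the intervals in the illustration shows how little such an error would alter the overall safety picture at this sample size.

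**What to change.** Add a paragraph to Section 12.5.2 along these lines:

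> For the Safety Set, CTCAE v5 grades will be derived from all collected values of ANC and lymphocytes (calculated from WBC and percentage where needed), WBC, hemoglobin, platelets, ALT, AST and total bilirubin, using each local laboratory's ULN. Shift tables will show baseline grade (Cycle 1 Day 1 or within 24 hours pre-dose) against worst grade from first dose to 30 days after last dose, with n, % and exact 95% CI for any worsening and for worsening to Grade 3 or above, alongside the adverse event tables.

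Shift from baseline is needed because Table 3-1 admits ALT/AST up to 3 × ULN, which Table 7-3 classes as Grade 1 once above ULN. Creatinine should be left out or footnoted, since Section 7.3.2 attributes its rise to an effect on tubular transporters with glomerular function unchanged. Lymphocytes and bilirubin go beyond the toxicities at issue and could be dropped to keep the tables short.

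The cost is one paragraph and a few tables, with no new tests or visits. Laboratory values and each site's reference ranges must be in the database. The documents do not clearly say that every value is entered, so some data entry may be added. Reported low-grade rates may rise, and laboratory-derived rates may differ from the adverse event tables, which calls for a footnote.

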9.1.4.8 Hematology

Hematology assessments of the parameters listed in Table 9-3 will be tested as per the schedule of assessments (Table 9-1).

9.1.4.9 Clinical chemistry and Creatinine clearance

Clinical chemistry and Creatinine clearance assessments of the parameters listed in Table 9-3 will be tested as per the schedule of assessments (Table 9-1).

9.1.4.10 Pregnancy and assessments of fertility

Women who are determined not to be of child bearing potential before the study will only be tested at screening. When non-child bearing potential status is determined during the study, further pregnancy testing will not be continued. Women are considered post-menopausal if they have had 12 months of natural (spontaneous) amenorrhea with an appropriate clinical profile (e.g. age appropriate, history of vasomotor symptoms), and otherwise not of child bearing potential if they have had surgical bilateral oophorectomy (with or without hysterectomy) or tubal ligation at least six weeks ago. In the case of oophorectomy alone, only when the reproductive status of the woman has been confirmed by follow up hormone level assessment is she considered not of child bearing potential.

The time windows granted for pregnancy testing are identical to the corresponding visit time windows for each visit.

If a positive pregnancy test is performed in between study visits, the patients must immediately notify the investigator.

9.1.4.11 General Guidance for Women of Child Bearing Potential and/or Use of Contraceptive Methods

Based on findings in animals, abemaciclib can cause fetal harm when administered to a pregnant woman. In animal studies, abemaciclib was teratogenic and caused decreased fetal weight at maternal exposures that were similar to human clinical exposure based on the area under the plasma concentration versus time curve (AUC) at the recommended human dose. Therefore, teratogenicity is considered an important potential risk for abemaciclib. There are no available human data informing the drug-associated risk. Advise pregnant women of the potential risk to a fetus. Additionally, there are no available data on effects of breastfeeding. Advise a nursing woman to discontinue breastfeeding during treatment with abemaciclib.

- A female of childbearing potential, must have a negative serum pregnancy test within 7 days of the first dose of abemaciclib and agree to use a highly effective contraception method during the treatment period and for 3 weeks following the last dose of abemaciclib.
- Contraceptive methods may include an intrauterine device [IUD] or barrier method. If condoms are used as a barrier method, a spermicidal agent should be added as a double barrier protection.
- Cases of pregnancy that occur during maternal exposures to abemaciclib should be reported. If a patient or spouse/partner is determined to be pregnant following abemaciclib initiation, she must discontinue treatment immediately. Data on fetal outcome and breast-feeding are to be collected for regulatory reporting and drug safety evaluation.

